Mean, Min, Median, Max, GeoMean, 95% CI: 3 significant digits

SD: 4 significant digits

CV%, GeoCV%: 1 decimal place

Definition of baseline:

The last measurement prior to first administration of trial treatment (either M3814, RT or Cisplatin) will be used as the baseline measurement.

Definition of treatment day:

Treatment Day 1 is defined as the date of first administration of trial treatment (M3814 and/or RT and/or Cisplatin), the day before is defined as Treatment Day –1 (no Treatment Day 0 is defined).

Definition of on-treatment evaluations for safety analyses:

On-treatment evaluations for safety analyses will be evaluations performed on or after Treatment Day 1 until 30 days after the last dose of trial treatment or the clinical cut-off date (if the treatment is still ongoing).

Definition of duration:

Duration will be calculated by the difference of start and stop date + 1 (e.g. survival time (days) = date of death – date of first dose + 1), if not otherwise specified.

Conversion factors:

The following conversion factors will be used to convert days into months or years:
1 month = 30.4375 days, 1 year = 365.25 days.

Data handling after cut-off date:

Data after cut-off do not undergo the cleaning process. The only exceptions are the date of death and the date last known to be alive. Data obtained after the cut-off will not be displayed in any listings or used for summary statistics (e.g. laboratory values of samples taken after data cut-off, AE with onset date after data cut-off, etc.) will not be included in any analysis or listing.

For any adverse event or concomitant medication starting before the cut-off date, the end date will not be imputed (even if the end date is after the cut-off date) and will be presented as filled in the eCRF at the time of the data export.

Handling of missing data:

For identification of AE treatment emergence, incomplete dates will be handled as follows:

- In case the onset date is completely missing or the onset is in the same year (if the onset year is available only) or the onset is in the same month and year (if the day is missing) as start of trial treatment then the onset date will be replaced by the minimum of start trial treatment and AE resolution date.

- In all other cases, the missing onset day or onset month will be replaced by 1.

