15.2 Adverse Events

All TEAEs will be summarized, i.e. those events that are emergent during treatment having been absent pre-treatment, or worsen relative to the pre-treatment state and with onset dates occurring within the first dosing day of trial treatment until 30 days after the last dose of trial treatment. If an adverse event started before treatment start and improved during treatment (i.e. with the same PT directly following, but lower grade) it should not be counted as a TEAE. However, if an adverse event started either before or during the treatment period and worsened during the treatment period this should be reported as a TEAE.

Counting rules and observation periods for AEs during the treatment period (TEAEs):

- The treatment period is defined from the first dosing day of trial treatment until 30 days after the last dose of trial treatment or the clinical cut-off date.
- If an AE is reported for a given subject more than once during treatment, the worst severity and the worst relationship to trial treatment will be tabulated.
- Adverse events related to trial treatment are those events with relationship missing, unknown or related to at least one treatment (M3814, RT or Cisplatin).
- Adverse events related to M3814 are those events related to M3814, regardless to relationship with RT and/or Cisplatin

- Adverse events related to RT are those events related to RT, regardless to relationship with M3814 and/or Cisplatin
- Adverse events related to Cisplatin are those events related to M3814, regardless to relationship with M3814 and/or RT
- In case a subject has events with missing and non-missing grades, the maximum of the non-missing grades will be displayed.

For identification of AE treatment emergence, incomplete dates will be handled using the rules presented in section 9.

AEs will be coded according to the current MedDRA. The severity of AEs will be graded using National Cancer Institute - Common Terminology Criteria for Adverse Events (NCI-CTCAE) version 4.03 toxicity grades.

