15.2.3 Late toxicities

A number of outputs will be produced for late adverse events. An adverse event is defined as late if it starts after the on-treatment period and it meets one of the following criteria:

- It is the first occurrence of adverse event for this participant on MedDRA preferred term level
- It is a recurring adverse event but there is gap between the end date of the previous occurrence and the start date of the re-occurrence (start date of reoccurrence – end date of previous occurrence > 0)
- It is a reccuring adverse event without gap between the end date of the previous occurrence and the start date of the re-occurrence and the grade has worsened:

The following will be produced for late toxicities:

- Table of all late toxicities by worst CTCAE grades: any grade (including AEs with missing grade), grades ≥ 3 , ≥ 4 and 5
- Listing of all late toxicities related to M3814
- Listing of all late toxicities related to radiotherapy
- Listing of all late toxicities grade ≥ 3

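### The late-toxicity rule treats a next-day continuation of the same event as a recurrence after a gap, so it counts as late even when its grade is unchanged or lower

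*SAP*

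**What the plan says.** SAP 15.2.3 sets an entry condition and three alternative criteria: "An adverse event is defined as late if it starts after the on-treatment period and it meets one of the following criteria".

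- Criterion 1: the subject has not had that preferred term before.
- Criterion 2: the term recurs after a gap, given as the formula "start date of reoccurrence – end date of previous occurrence > 0".
- Criterion 3: the term recurs "without gap between the end date of the previous occurrence and the start date of the re-occurrence and the grade has worsened".

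The on-treatment period comes from SAP section 9: "evaluations performed on or after Treatment Day 1 until 30 days after the last dose of trial treatment". The same section fixes how days are counted, unless specified otherwise: "Duration will be calculated by the difference of start and stop date + 1". The stop date is therefore itself a day with the event.

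The outputs of 15.2.3 are a table of late toxicities by worst grade (any, ≥3, ≥4 and 5) and three listings: related to M3814, related to radiotherapy, and grade ≥3.

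**The concern.** Criterion 3 has a purpose only if a contiguous continuation is meant to count as late when it worsens and not otherwise. Criterion 2 undercuts that for records dated on consecutive days. Such records have no event-free day between them, yet they pass the gap test, and criterion 2 puts no condition on grade.

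The situation can plausibly arise here. In the schedules of assessments (Protocol Tables 1 to 6), adverse event assessment at the mid-term and long-term visits is directed at treatment-emergent events that are still ongoing. Records made after day 30 can therefore include acute toxicity that is resolving. Protocol 3.6 describes late toxicities as those arising 3 months or more after the end of RT, which is a different thing. Where the effect occurs, the same clinical course is late or not late according to which of two adjacent dates was entered, and the error runs toward overstating late toxicity.

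**Working it through.** **Inputs.** The gap formula and the three criteria are from SAP 15.2.3. The end of the on-treatment period (last dose + 30 days) and the inclusive day count are from SAP section 9. Whether a changed grade is dated on the old record's stop date or on the next day is not in the documents, so both cases are worked. The SAP states no figure to reproduce.

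**Formulas.** Let the previous record end on day e and the new record start on day s.

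- Test as written: gap if s − e > 0.
- Event-free days under the inclusive count: s − e − 1.

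**Check of the day count.** Take Grade 2 on days 1 to 10 and Grade 1 on days 11 to 20. The durations are (10 − 1 + 1) + (20 − 11 + 1) = 10 + 10 = 20 days. The whole span is 20 − 1 + 1 = 20 days. The records fill the span with no free day, yet s − e = 11 − 10 = 1 > 0, so the test reports a gap.

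**All cases, for a new record starting more than 30 days after last dose and a previous grade of 2:**

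| s − e | Event-free days | New grade | Late as written | Late if a gap is s − e > 1 |
|---|---|---|---|---|
| 0 | none (shared day) | 1 | no | no |
| 0 | none (shared day) | 2 | no | no |
| 0 | none (shared day) | 3 | yes (criterion 3) | yes (criterion 3) |
| 1 | 0 | 1 | **yes (criterion 2)** | **no** |
| 1 | 0 | 2 | **yes (criterion 2)** | **no** |
| 1 | 0 | 3 | yes (criterion 2) | yes (criterion 3) |
| 2 | 1 | 1, 2 or 3 | yes (criterion 2) | yes (criterion 2) |

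Only the two bold rows change. An overlapping record (s − e < 0) is also without a gap under either threshold.

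**Entry condition.** A next-day improvement that starts 20 days after last dose is not late under either threshold, because 20 ≤ 30.

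**Illustration.** Mucositis is Grade 3 until post-treatment day (PTD) 33, then Grade 2 until PTD 60. Entered from PTD 34: 34 − 33 = 1 > 0, so late. Entered from PTD 33: 33 − 33 = 0, so criterion 3 applies, the grade has not worsened, and the record is not late.

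**Partial dates.** Section 9 gives imputation rules for identifying treatment emergence: "In all other cases, the missing onset day or onset month will be replaced by 1", and a missing stop day becomes the last day of the month. If the same rules were used for 15.2.3, which the SAP does not say, a stop in May and a start in June with both days missing would become 31 May and 1 June. The difference is 1, and an improved record would count as late.

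**Where it shows.** A Grade 3 to Grade 2 step-down enters the any-grade column and, if related, the M3814 or RT listing. The grade ≥3 outputs change only when the continuing record is itself Grade 3 or higher, for example Grade 4 to 3 or an unchanged Grade 3. DLTs are analysed separately in SAP 15.1.

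**The case against.** The strongest reply is that the rule is correct if sites close the old record and open the new one on the same date. A continuation then gives 0 and goes to criterion 3, while any positive difference is a real interruption. That criterion 3 exists at all suggests the authors expected differences of 0. Protocol 7.4.1.2 refers recording detail to sponsor eCRF conventions that are not part of these documents, so this reading cannot be excluded. It stands, and it makes the concern conditional on the dating practice.

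Two supporting arguments are also weaker than they look. Section 9 defines duration, with room for exceptions. It does not define a gap between records, so there is no direct contradiction with 15.2.3. And the sentence in SAP 15.2 about an improved event, "i.e. with the same PT directly following, but lower grade", concerns events that began before treatment. It helps on intent by analogy only, and does not say whether the following record starts on the same day or the next.

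The change also has a downside. With same-day dating, a record starting the next day could be a true new episode, and a threshold of 1 would drop it from the table unless it had worsened. That is undercounting in a safety output. The downside is small, and the outcome of each event, which the listing in SAP 15.2.1 already includes, can be used to avoid it.

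Finally, the listing of all adverse events prints terms, dates and grades, so contiguous records can be seen by a reader who looks.

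**Conclusion.** The point holds as a minor weakness in a descriptive secondary safety output. As written, a record of the same preferred term that starts more than 30 days after last dose, and on the day after the previous record ended, is late even if its grade is unchanged or lower. The SAP's own day count finds no event-free day there, and criterion 3 shows that contiguous records were meant to count only on worsening.

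The size cannot be given. It depends on how often grade changes after day 30 are dated from the next day, and the documents do not say.

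A reader might infer that the late-toxicity table will be inflated, that every resolving acute toxicity will be caught, or that sites will differ. The documents support none of these. Improvements within 30 days of last dose are excluded by the entry condition, same-day dating is unaffected, and recording follows conventions issued by the sponsor, with nothing to show that sites apply them differently.

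**What to change.** In SAP 15.2.3:

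- Define a gap as start of the re-occurrence minus end of the previous occurrence > 1 day, meaning at least one event-free day.
- Apply criterion 3 to differences of 1 day or less, so that these records are late only if the grade worsened.
- Add one exception: keep counting a next-day record as a recurrence when the previous record's outcome is recovered/resolved.

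The documents name the outcome field but do not list its categories. Before relying on the exception, check how sites code the outcome of a record that is closed only because the grade changed. It would also help to state the eCRF dating convention for grade changes in the SAP, and to say whether the section 9 date imputation applies here.

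The cost is a short text edit and a few lines of code. No new data are needed. Same-day continuations and recurrences after at least one free day are classified as before.

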5.1.1 Dose Escalation Rules

The criteria for dose escalation are based on the occurrence of AEs and/or DLTs that are unrelated to underlying conditions and/or to concomitant medication during the DLT period in evaluable subjects in each cohort. The DLT window of 5 weeks (Phase Ia, Arm A) or 12 weeks (Phase Ia, Arm B and the first 3 subjects in the expansion cohort for Arm A [NSCLC]) after the start of M3814 treatment allows an evaluation of acute toxicity. M3814 dose escalation will not proceed to the next dose level until all subjects in the previous dose level have been observed for the duration of the DLT period. However, RT/CRT and the combination of RT/CRT and M3814 can also give rise to later toxicities. A 3-month mid-term safety follow-up will be performed in all subjects in the Phase Ia part of the trial and, once available, these data will also guide subsequent dose escalation and the establishment of the RP2D. Available PK and PD data will also be taken into consideration.

Dose Escalation During Phase Ia

A Bayesian two-parameter logistic regression model with overdose control will be used to assist the SMC with dose selection during the Phase Ia dose escalation (capsule formulation in Arm A/B, and tablet formulation in Arm B). Cohorts of 3 subjects each will be treated at the same dose level (capsule starting dose: 100 mg QD for Arm A and 50 mg QD for Arm B). The model incorporates prior information (from nonclinical data) and observed information from each completed cohort (and data from all previous cohorts) to provide a recommended dose for the next cohort. A preselected set of acceptable doses are considered by the model, however doses which are not part of the prespecified set may be chosen as well. The model ensures that recommended doses correspond to a probability of less than 25% that the true DLT rate is more than 35% in Arm A and 45% in Arm B. Dose escalation will stop in each arm as soon as the first of the following stopping rules apply: a maximum of 30 subjects are included, more than three cohorts are assigned to the same dose level, or the estimate of DLT probability at the MTD reaches a sufficient precision (see Section 8 for more details).

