6.1 Secondary safety analysis

Cut-off date:

This IAP covers the analyses for efficacy and safety based on the data cut-off (see also chapter 9 Data handling after cut-off date). Statistical analyses will be performed using cleaned eCRF data gained up to a clinical cut-off date which is determined when last subject has reached the second post-treatment tumor assessment.

The cut-off date is determined once a data extract (before data base lock) is available which indicates that the last subject has reached the second post-treatment tumor assessment. The clinical cut-off date will be the date on which according to this data extract the last subject has reached the second post-treatment tumor assessment.

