8.2 Definition of Analysis Sets and Subgroups

All Subjects Analysis Set (ALL):

The All subjects (ALL) analysis set will include all the subjects who have signed the ICFs (i.e., screening failures plus subjects enrolled).

Safety Analysis Set (SAF):

The Safety analysis set will include all subjects who receive at least one administration of the trial treatment (either M3814, RT or Cisplatin).

Full Analysis Set (FAS):

The Full Analysis Set will include all subjects who receive at least one administration of the trial treatment.

Dose Escalation Analysis Set (DE) :

The Dose Escalation (DE) analysis set will include all subjects treated in dose escalation cohorts who receive at least 80% of M3814 and RT planned dose and complete the DLT period (through 5 weeks [Phase Ia, Arm A] or 12 weeks [Phase Ia, Arm B] after start of M3814 treatment). The DE set will also include subjects treated in dose escalation cohorts who experience a DLT during the DLT period regardless of the received amount of each drug.

Pharmacokinetics Analysis Set (PK):

The PK evaluation (PK) analysis set in Phase Ia and Phase Ib parts will include subjects who have received at least the first dose of the drug and provided PK samples as per protocol for at least 6 hours following first dosing on Fraction Day 1.

Table 1: Summary of analyses and associated analysis set

Analyses	ALL	SAF	FAS	DE	PK
Disposition and deaths	✓				
Baseline Assessments		✓			
Past and Concomitant Therapies		✓			
Compliance and Exposure		✓			

CONFIDENTIAL
INFORMATION

12/60

Analyses	ALL	SAF	FAS	DE	PK
Primary endpoint: DLTs				✓	
Secondary efficacy endpoints			✓		
Safety and tolerability		✓			
Biomarker		✓			
Pharmacokinetics					✓

9

General Specifications for Data Analyses

Statistical analyses will be performed with SAS 9.4 or higher.

Pooling of centers:

Because of the anticipated small number of subjects enrolled in each center, data will be pooled across centers, and the factor center will not be considered in statistical models or for subgroup analyses.

Presentation of continuous and qualitative variables:

All outputs will be provided for each arm separately. No data between arms will be pooled, unless otherwise stated. For each arm, data will be presented by formulation, dose level and overall unless specified otherwise. The dose level will be defined by the planned dose of the corresponding cohort. If several cohorts have same dose level, there will be pooled together for all summary outputs.

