Continuous variables will be summarized using descriptive statistics, i.e.

- Number and percentage of subjects (n (%)), number and percentage of subjects with missing values (Missing (%))
- Mean, 95% confidence intervals, as appropriate
- Standard deviation
- Median
- Q1, and Q3
- Minimum, and maximum

If there are no missing values, this should be indicated by a 0 (0.0).

Missing statistics, e.g, when they cannot be calculated, should be presented as “nd”. For example, if n=1, the standard deviation cannot be computed and should be presented as “nd”.

Qualitative variables will be summarized by frequencies and percentages.

Unless otherwise stated, the calculation of proportions will be based on the number of subjects of the analysis set of interest. Therefore, counts of missing observations will be included in the denominator and presented as a separate category.

Presentation of PK Concentration Data

M3814 and **CCI** concentration data will be descriptively summarized using: number of non-missing observations (n), arithmetic mean (Mean), standard deviation (SD), coefficient of variation (CV%), minimum (Min), median (Median) and maximum (Max). In $n \leq 2$, only n, Min, and Max will be reported.

Descriptive statistics of PK concentration data will be calculated using values with the same precision as the source data, and rounded for reporting purposes only. The following conventions will be applied when reporting descriptive statistics of PK concentration data:

Mean, Min, Median, Max: 3 significant digits

SD: 4 significant digits

CV%: 1 decimal place

Presentation of PK Parameter Data

Pharmacokinetic parameter data will be descriptively summarized using: n, Mean, SD, CV%, Min, Median, Max, geometric mean (GeoMean), and the geometric coefficient of variation (GeoCV). For time to reach maximum observed concentration (t_{max}), only n, Min, Median, and Max will be reported.

The PK parameter maximum observed plasma concentration (C_{max}) will be reported with the same precision as the source data. All other PK parameters will be reported to 3 significant figures. In export datasets, as well as in the SDTM PP domain, PK parameters will be provided with full precision, and will not be rounded. Descriptive statistics of PK parameter data will be calculated using full precision values, and rounded for reporting purposes only.

The following conventions will be applied when reporting descriptive statistics of PK parameter data:

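### The late-toxicity table counts subjects who never reached the late window as free of late toxicity, and at the secondary safety cut-off it sets columns with unequal follow-up side by side without showing that follow-up

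*SAP*

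**What the plan says.** SAP Section 15.2.3 opens its definition with: "An adverse event is defined as late if it starts after the on-treatment period and it meets one of the following criteria". The on-treatment period, defined in SAP Section 9, runs "until 30 days after the last dose of trial treatment or the clinical cut-off date (if the treatment is still ongoing"). Section 15.2.3 then plans one summary table, the "Table of all late toxicities by worst CTCAE grades", and three listings (related to M3814, related to radiotherapy, and Grade 3 or higher). Unlike the sections on either side of it, it names no analysis set.

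The default comes from elsewhere. SAP Section 9: "Unless otherwise stated, the calculation of proportions will be based on the number of subjects of the analysis set of interest"; missing observations stay in the denominator. SAP Table 1 assigns safety to the SAF, which requires one administration of any trial treatment and no minimum follow-up. SAP Section 9 also presents data by arm, formulation, dose level and overall.

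Two milestones use this table. SAP Section 6.1 sets the secondary safety cut-off at the time "when last subject has reached the second post-treatment tumor assessment". SAP Section 6.2 allows the final analysis only once the last subject has a full year of follow-up. Protocol Section 7.4.1.3 collects adverse events to PTD 365.

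**The concern.** A late event can be recorded only in a subject still under observation more than 30 days after the last dose. Anyone who died or withdrew earlier adds to the denominator but can never add to the numerator. The percentage therefore answers a different question from the one a reader will bring to it: how often late toxicity occurs among patients who live long enough to be exposed to it.

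The second difficulty is confined to the secondary safety analysis. Dose levels open in sequence, so at a common calendar cut-off the recently enrolled levels have been watched for less of the late window than the early ones. Crude percentages by dose level then mix risk with length of observation, and nothing beside them shows which is which. For a radiosensitiser, late damage to normal tissue is a central safety question, and SAP Section 4 sends these results to the trial report, submissions and manuscripts.

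**Working it through.** The plan states no late-toxicity rate, so there is no figure to reproduce on that point. The nearest documented figure is the 10% allowance for subjects not evaluable for DLT in Phase Ia (Protocol synopsis). It reproduces: 78/0.90 = 86.7, rounded up to 87, and 87 + 54 + 23 = 164 against the stated approximately 165.

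**1. Denominator.** Rate on SAF = rate among those entering the late window × share entering.
- With 10% early loss (proxy), 10%, 20% and 30% appear as 9%, 18% and 27%.
- With an assumed early loss of 5% to 30%, a rate of 30% appears as 28.5% to 21%.
- In small cells, one event among 6 treated with 5 at risk is 16.7% against 20.0%; among 3 treated with 2 at risk it is 33.3% against 50.0%.

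**2. Length of observation at the secondary cut-off.** The late window is PTD 31 to 365, or 365 − 30 = 335 days. Tumor assessments are 6-weekly at PTD 42, 84, 126 and 168 (Protocol Tables 1, 2 and 5), so the second is PTD 84. The last subject then has 84 − 30 = 54 days, and 54/335 = 16%. Assume a constant hazard λ = −ln(1 − R)/335, where R is the full-window risk. The risk visible in 54 days is 1 − exp(−54λ): 1.7%, 3.5% and 5.6% for R = 10%, 20% and 30%. Protocol Section 3.6 places late radiation toxicity at 3 months or later (3 × 30.4375 = 91 days), so a constant hazard may overstate what is visible by PTD 84.

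**3. Both together, Arm A.** Assume R = 20% and exponential survival with k = ln 2/median. The late window opens about Day 42 (RT ends about Day 12), so the share entering is s = exp(−42k). The observed proportion on SAF over T late-window days is s × λ/(λ + k) × [1 − exp(−(λ + k)T)]; dividing by s gives the proportion among those entering.

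| Assumed median survival (months) | Share entering | T = 335: SAF / entering | T = 54: SAF / entering |
|---|---|---|---|
| 3 | 73% | 5.5% / 7.6% | 2.1% / 2.9% |
| 6 | 85% | 9.9% / 11.6% | 2.7% / 3.2% |
| 12 | 92% | 13.8% / 15.0% | 3.1% / 3.4% |
| 24 | 96% | 16.6% / 17.2% | 3.3% / 3.4% |

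For Arm B, with the late window opening about Day 77, the share entering is 86% and 93% at medians of 12 and 24 months.

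Within each pair, the gap is the denominator effect. Between the last two columns, the gap is the follow-up effect: at a 6-month median, two dose levels with the same hazard would show 9.9% and 2.7% on SAF if one had the full window and the other only 54 days. Changing the denominator moves the second figure only to 3.2%, so it does not repair the cut-off deficit. At the final analysis every subject has T = 335 available, and the last column no longer applies.

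**The case against.** The strongest reply is that this is a descriptive phase I table, that follow-up is visible elsewhere, and that larger claims fail. Much of that stands.

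- **Dose order.** A reader might infer that late toxicity is understated most at the highest doses. The documents do not support this. SAP Section 6 allows de-escalation and extension at the same dose, SAP Section 9 pools cohorts at the same dose, and tablet cohorts start at 100 mg while the 300 mg capsule dose was under test (Protocol Section 5.1.2). Nothing says that early death or withdrawal is more frequent at high doses.
- **Final analysis.** A reader might infer that the cut-off deficit persists. It does not, because SAP Section 6.2 waits for the full year. A reader might also treat late-window person-time lost to death in Arm A as bias at that analysis. With full potential follow-up and no withdrawals, a cumulative incidence with death as competing event equals the crude proportion among those entering, so the lost person-time is not bias in that quantity.
- **Recommended Phase II dose.** Protocol Section 5.1.1 says "these data will also guide subsequent dose escalation and the establishment of the RP2D", but there it refers to the 3-month mid-term safety follow-up. The Safety Monitoring Committee works from a separate analysis plan (SAP Section 4). Nothing shows that this table drives dose selection.
- **Other outputs.** Disposition by dose level, time on trial, the swimmer plots and deaths within 30 days of last dose let a reader reconstruct much of who entered the late window. But none gives the number at risk or the time observed beside the late-toxicity percentages, and the swimmer plot runs to death or last date known alive, not to the last late-event assessment.
- **Inference.** The all-treated denominator is read from SAP Section 9 and Table 1; Section 15.2.3 does not state it. That is a reason to state the denominator there.

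**Conclusion.** The point holds in two limited parts. First, at both milestones the default denominator includes subjects who could not have a late event, and the rate among those at risk is understated by the share not entering the late window. The size is about 10% relative on the only attrition figure in the protocol. That figure concerns DLT evaluability, and in Arm A the DLT period ends at PTD 21, before the late window opens, so it is a proxy only. Under the assumed survival medians of 3 to 24 months the share missing in Arm A runs from 27% to 4%; 3 months is an extreme choice, since Protocol Section 5.3.1 requires a life expectancy of at least 3 months at entry.

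Second, at the secondary safety cut-off alone, recently enrolled dose levels have shorter late follow-up, down to 54 of 335 days for the last subject, so crude percentages cannot be compared across dose levels. The 54 days is the last subject's figure; others at that level may have more. The hazards and survival times are assumptions, used only to show scale.

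**What to change.** In SAP Section 15.2.3, state the denominator as SAF subjects followed beyond 30 days after the last dose. Show, for each dose level, the number entering the late period and their late follow-up time. At the secondary safety cut-off, label the table as based on incomplete follow-up and add late events per person-month or a cumulative incidence with death as competing event, for any grade and for Grade 3 or higher, pooled by arm where dose groups are small.

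The cost is a few sentences and one or two columns built from dates already collected. The downside is that rates become slightly higher and less precise in small dose groups. The new denominator alone does not correct the cut-off deficit; the follow-up time and the time-based summary are needed for that.
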